We aim to characterize the safety and efficacy of a topical preparation of *Lactobacillus sp.*, honey, and turmeric in an emollient base in restoring the scalps of those with dry scalp to more closely resemble the healthy scalps.

2. STUDY DESIGN AND SYNOPSIS:

This pilot study consists of participants diagnosed with dry scalp. Participants will receive the required topical vehicle with the treatment condition (containing dead bacteria) on their scalp. This study will consist of 15-40 participants' ages 1 years old to 17 years old and 20-40 participants 18 and older with a clinical diagnosis of dry scalp. Participants will be recruited either while visiting a dermatologist for a standard office visit, while visiting a pediatrician for a standard office visit, or by coming into Children's Healthcare Associates, Medical Dermatology, or our Northwestern research office to be assessed by a physician. Each study visit will take approximately 15-20 minutes.

No randomization will occur, as all participants will receive the active treatment. Each adult participant will apply the active treatment once daily for a study period of 14 days and discontinue using all other scalp management therapies. Each child participant (with the help of a caregiver, if needed) will apply the active treatment once every 2 to 3 days for a study period of 14 days and discontinue using all other scalp management therapies.

The primary goal of this study is to determine the safety and effectiveness of *Lactobacillus sp.*, honey, and turmeric in reducing dry scalp symptomology.

There are three goals in the comparison of these conditions:

- The first is to find the effectiveness of the active treatment in improving clinical disease severity. To accomplish this, an investigator will assess the severity of dry scalp before and after the treatment period using the 11-point flaking scale (Neumann 1996), respectively.
- The second goal is to determine whether the active treatment is safe. This will be accomplished by contacting the patient via over the phone and through daily emails designed to document adverse events and Overall Safety Score. The Overall Safety Score is a 4-point assessment ranging from "no signs of irritation" (0) to "patient discontinued due to irritation" (3). Participants will be asked about the Overall Safety score at the halfway point and the end point of the study.
- The third exploratory goal is to determine whether the microbiome can be changed. This will be

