accomplished by obtaining swab samples from the participants' scalps, before and after the treatment period. The samples will be analyzed using 16s RNA sequencing and internal transcribed spacer (ITS) sequencing. Additionally, the change in colony count of bacterial and fungal colonies on the scalp before and after the treatment will be assessed using the Replicate Organism Detection and Counting (RODAC) method. We aim to characterize the effects of *Lactobacillus* sp., honey, and turmeric on dry scalps.

- Finally, this study will determine the quality of life of participants before and after the treatment period. Quality of life will be calculated using the ScalpDex tool, a validated 23-item instrument that explains the way that patients with scalp dermatitis are affected by symptoms, functioning, and emotions.

3. STUDY OBJECTIVES:

The first goal of this study is to determine the effectiveness of introducing *Lactobacillus* sp., honey, and turmeric, in reducing dry scalp symptomology.

Hypothesis 1a: Participants' scalps treated with vehicle plus *Lactobacillus* sp., honey, and turmeric preparation will exhibit decreased dry scalp severity on assessment by an investigator when compared to the scalps before treatment, as measured by an 11-point flaking scale.

The next objective is to determine the safety of introducing *Lactobacillus* sp., honey, and turmeric, in reducing dry scalp symptomology

Hypothesis 2a: The product containing *Lactobacillus* sp., honey, and turmeric will be safe for participant's scalps as measured by the Overall Safety Score and patient logs.

The final objective of this study is to compare the determine if an active *Lactobacillus*, honey, and turmeric topical preparation changes the microbiome after use for a dry scalp condition to more closely resemble healthy scalp

Hypothesis 3a: Participants' scalps treated with the active *Lactobacillus*, honey, and turmeric preparation will have a microbiome similar to those with healthy scalps.

4. STUDY POPULATION:

We aim to recruit participants with diagnosed dry scalp and with clinical signs on the scalp. Recruitment will consist of male and female participants. This will include 15-40 children between the ages of 1 year to 17 years old, and 20-40 adults over the age of 18.

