4.1.2. Exclusion criteria

- e. Infants younger than 1 year old
- f. Patients diagnosed with other scalp diseases such as psoriasis, tinea capitis, and pediculosis capitis
- g. Systemic steroid or oral antibiotic use during the past two months
- h. Allergy to any of the preparation components

5. STUDY PROCEDURES:

For this study, 20-40 subjects over the age of 18 and 15-40 subjects aged 1 year to 17 years, all with a clinical diagnosis of dry scalp, will be enrolled. 5-10 adults participants will be enrolled and complete the study prior to enrolling children. All participants who fit the inclusion criteria and are currently being seen at either a Lurie Children's location, Children's Health Associates, the Medical Dermatology Associates of Chicago, or other outside locations, will be verbally invited to participate in the study, immediately following their regularly scheduled appointment, by a study coordinator will be administered informed consent. Additionally, those not able to attend a standard office visit, will come into our Northwestern office to be assessed by a board-certified physician. Study staff will identify potentially eligible study patients from clinic databases or those who have previously shown interest and mail or email these patients a letter with information on the study protocol, eligibility criteria and participant compensation, as well as instructions to contact study staff if interested in participation. We will also wait a week after mailing the potentially eligible study patients and call and/or e-mail them to see if they are interested in participation.

A research coordinator will obtain bilateral culture swabs of the scalp, in order to assess the composition of the local bacterial community. A research coordinator will also obtain bilateral cultures of each participant's scalp via the RODAC plate method in order to assess the burden of *S. aureus* on the skin. Swab and culture samples will be sent to the lab of [name] at Lurie Children's or to [name] lab at Rush University to be processed via 16s rRNA sequencing and colony count, respectively. Lastly, a board-certified physician will assess the clinical severity of the participant's dry scalp via the 11-point flaking scale. Photographs will be taken as record for both adult and child studies.

Each participant will then fill out a baseline survey including demographics in REDCap.

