6.1. Primary Outcome Measures

The primary objective is to determine the safety and efficacy of YoBee in improving dry scalp conditions. Efficacy will be determined using the Investigator's Global Assessment (IGA) scale (Table 1), a 5-point assessment ranging from clear (0) to severe disease (4) and the Total Severity Scale (TSS) (Table 2), an assessment that averages erythema, scaling, and pruritus severity scores of scalp lesions. The TSS uses a 4-point scale ranging from none (0) to severe (3). Lastly, photographs of the scalp will be collected before and after treatment. Safety will be determined by contacting the patient via over the phone or through email to document adverse events and Overall Safety Score. The Overall Safety Score (Table 4) and the reporting of adverse events throughout the study will measure the safety of YoBee. The Overall Safety Score is a 4-point assessment ranging from “no signs of irritation” (0) to “patient discontinued due to irritation” (3). Participants will include the Overall Safety Score assessment in their daily journal.

An exploratory aim of this study is to find whether YoBee changes the microbiome after use for a dry scalp condition to more closely resemble healthy scalps. This will be accomplished by obtaining swab samples from the participants' scalps, before and after the treatment period. The samples will be analyzed using 16s RNA sequencing and internal transcribed spacer (ITS) sequencing. Additionally, the change in colony count of bacterial and fungal colonies on the scalp before and after the treatment will be assessed using the Replicate Organism Detection and Counting (RODAC) method. Finally, ScalpDex, a validated instrument, will assess the change in quality of life of participants. ScalpDex is a 23 question survey that will be administered electronically via RedCap to participants.

7. DATA DISCLOSURE AND SUBJECT CONFIDENTIALITY:

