8. EFFICACY ASSESSMENT

The efficacy of our trial will be measured by an 11-point scalp flaking scale (IGA). Second, we will employ 16S rRNA gene sequencing to analyze the composition of the scalp microbiome before and after treatment. Finally, efficacy toward reducing Staph colonization will be quantified via colony count of *S. aureus* scalp

cultures from patients plated on RODAC plates, and compared against each patient's baseline measurements.

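### Hypothesis 3a claims a microbiome like that of healthy scalp, but the available plan has no healthy reference or similarity measure, so the samples can show only change from baseline

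*Combined protocol and SAP*

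**What the plan says.** Three statements tie the microbiome to healthy scalp.

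- Section 3, Hypothesis 3a: treated scalps with the "turmeric preparation will have a microbiome similar to those with healthy scalps".
- Section 3, final objective: whether the "topical preparation changes the microbiome after use for a dry scalp condition to more closely resemble healthy scalp".
- Section 6.1, exploratory aim: whether "YoBee changes the microbiome after use for a dry scalp condition to more closely resemble healthy scalps".

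The synopsis in section 2 is more modest: "The third exploratory goal is to determine whether the microbiome can be changed".

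On design, section 2 states: "No randomization will occur, as all participants will receive the active treatment". Section 5 describes the adults and children as "all with a clinical diagnosis of dry scalp, will be enrolled". On analysis, section 8 says "we will employ 16S rRNA gene sequencing to analyze the composition of the scalp microbiome before and after treatment", and it compares *S. aureus* colony counts with each participant's own baseline. Section 10 gives units for the microbiome measures (percentage of 16S tags, picograms of bacterial DNA, colony-forming units per area) and no comparison. The power statement in section 10.1 concerns a severity score only.

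**The concern.** A claim of similarity to healthy scalp is a claim against an external standard. It needs that standard, a way to measure distance from it, and a limit below which two communities count as similar. Hypothesis 1a, in the same section, names both its comparison (the scalp before treatment) and its measure (the flaking scale). Hypothesis 3a names neither a source for the healthy standard nor a measure.

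If the plan is followed exactly, Hypothesis 3a can be neither supported nor refuted. The practical risk is in reporting: a before/after shift could be presented as the scalp having become like healthy scalp, although no healthy scalp was examined.

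**Working it through.** No figure in the plan relates to Hypothesis 3a, so there is nothing to reproduce. Without a reference, a margin or a variance, no sample size or power for similarity can be computed. The check compares what each form of the claim needs with what the plan collects.

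**1. What each claim needs.** Let B be a participant's baseline profile, P the day-14 profile, H the healthy profile and d a distance between profiles.

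- Similar to healthy: d(P, H) below a margin set in advance. Needs H, d and the margin.
- Closer to healthy: d(P, H) < d(B, H). Needs H and d.
- Changed: P compared with B. Needs paired samples only.

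**2. Where H could come from.**

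- *Healthy participants:* none. Sections 2, 4 and 5 enrol only people with dry scalp.
- *A comparison arm:* none. Section 2 describes a single treated group.
- *An unaffected site on the same person:* none designated. Section 5 asks for swabs from both sides of the scalp without separating affected from unaffected areas.
- *An external data set:* none named. The background cites studies of healthy and diseased skin, but no section makes any of them a reference for analysis.

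**3. Whether d or a margin is defined.** Sections 8 and 10 contain neither. A non-significant difference from healthy would not fill the gap, because failing to find a difference does not show similarity.

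**4. What can be computed.** H is absent, so the first two forms fail. The third can be computed from the planned samples and matches the synopsis goal. Section 10 names no test even for that.

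**5. How far the background helps with the softer claim.** It reports that affected skin is dominated by *Staphylococcus* and less diverse than neighbouring unaffected skin, and section 8 plans a *Staphylococcus* readout. This gives an expected direction. It gives no healthy value for the scalp, and the same section calls the precise link between dysbiosis, eczema and dry scalp unclear. A fall in *Staphylococcus* or a rise in diversity would therefore be indirect evidence, and uncontrolled, since there is one arm.

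**6. Who contributes pairs (a separate, minor point).**

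- *No day-14 sampling listed for children:* the narrative in section 5 gives repeat swabs and RODAC cultures for adults and only a physician assessment for children. The child paragraph in section 6 lists the flaking survey and a questionnaire.
- *No age limit on sampling:* the third goal in section 2, the Visit 2 schema in section 5, the paragraph in section 5 that repeats the coordinator's duties at visit 2, the general day-14 paragraph in section 6, and section 6.1.

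The upper limit on pairs, before dropout or failed samples, follows from the enrolment ranges:

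- adults only: 20 to 40
- adults and children: 20 + 15 = 35 to 40 + 40 = 80

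**The case against.** The strongest reply is that this is loose wording under an exploratory aim in a single-arm pilot. The synopsis already states a testable goal, section 8 plans only before/after comparison, and over-claiming in a later report is a possibility rather than a fact. This limits the seriousness of the point but does not remove it. Hypothesis 3a is still one of the protocol's three numbered hypotheses, and section 8 lists microbiome composition and staphylococcal counts under efficacy.

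A second reply is that the background supplies the healthy comparison, and that it is more specific to scalp than it first appears. It cites a study of the scalp microbiome in dandruff and seborrheic dermatitis, and inclusion requires dandruff symptoms. The sentence calling the link unclear also concerns the exact relation among dysbiosis, eczema and dry scalp, not whether healthy and diseased communities differ. All of that stands as support for a direction. It does not make the cited study a planned reference with values, a measure and an analysis.

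A reader might also count the opening aim, "restoring the scalps of those with dry scalp to more closely resemble the healthy scalps", as a fourth microbiome statement. The text does not support that: it speaks of the scalp in general and does not mention the microbiome.

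**Conclusion.** The point holds. Three statements refer the microbiome to healthy scalp, and the available text contains no healthy reference, similarity measure or margin. Similarity cannot be tested, and movement toward healthy scalp can be supported only indirectly. It should be corrected, but it touches an exploratory aim only.

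Three stronger readings are not supported.

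- A reader might infer that the trial's main conclusions are compromised. Primary efficacy and safety do not depend on Hypothesis 3a.
- A reader might infer that the trial needs a healthy control group. It needs one, or another reference fixed in advance, only if the sponsor keeps the healthy-scalp claim.
- A reader might infer that children are not sampled at day 14. The sections conflict, and several set no age limit, so this is unresolved.

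The conclusion rests on absence. Two parts of the document were not available: the text before the surviving background, and the text between sections 11 and 13. The sections where a reference would be expected (population, procedures, data collection, efficacy, statistics) were available and contain none.

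**What to change.** Reword Hypothesis 3a, the final objective in section 3 and the exploratory aim in section 6.1 to the synopsis goal. Define it as within-participant change from baseline to day 14 in the measures already planned: 16S composition and diversity, ITS sequencing, total bacterial DNA by quantitative PCR, and RODAC counts. While editing, align the descriptions of these measures. ITS appears in sections 2 and 6.1 but not in sections 5, 8 or 10. RODAC counts are described as *S. aureus* in sections 5 and 8 but as bacterial and fungal colonies in sections 2 and 6.1.

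Add a sentence that such change will not be reported as similarity to, or restoration of, healthy scalp, and that a fall in *Staphylococcus* or a rise in diversity is indirect, uncontrolled evidence.

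The cost is wording in three places and a narrower exploratory claim, with no added procedures. Keeping the healthy-scalp claim would be a larger change: a healthy reference, a similarity measure and a margin, all fixed in advance.

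Separately, reconcile the passages in sections 2, 5, 6 and 6.1 on day-14 sampling of children. If children are not sampled then, state that the change analysis covers adults only. That adds no procedures but limits the analysis to at most 20 to 40 pairs.

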4.1.1. Inclusion criteria

- a. Age 1 year (or corrected age of 1 year, for those born prematurely) to 17 years for children, and adults 18 and older
- b. Patients with dry scalp and dandruff symptoms as determined by a board-certified Dermatologist, Allergist, or Pediatrician
- c. Good general health
- d. Participant and/or their parents are able to read, write, and understand study materials in English

4.1.2. Exclusion criteria

- e. Infants younger than 1 year old
- f. Patients diagnosed with other scalp diseases such as psoriasis, tinea capitis, and pediculosis capitis
- g. Systemic steroid or oral antibiotic use during the past two months
- h. Allergy to any of the preparation components

5. STUDY PROCEDURES:

For this study, 20-40 subjects over the age of 18 and 15-40 subjects aged 1 year to 17 years, all with a clinical diagnosis of dry scalp, will be enrolled. 5-10 adults participants will be enrolled and complete the study prior to enrolling children. All participants who fit the inclusion criteria and are currently being seen at either a Lurie Children's location, Children's Health Associates, the Medical Dermatology Associates of Chicago, or other outside locations, will be verbally invited to participate in the study, immediately following their regularly scheduled appointment, by a study coordinator will be administered informed consent. Additionally, those not able to attend a standard office visit, will come into our Northwestern office to be assessed by a board-certified physician. Study staff will identify potentially eligible study patients from clinic databases or those who have previously shown interest and mail or email these patients a letter with information on the study protocol, eligibility criteria and participant compensation, as well as instructions to contact study staff if interested in participation. We will also wait a week after mailing the potentially eligible study patients and call and/or e-mail them to see if they are interested in participation.

A research coordinator will obtain bilateral culture swabs of the scalp, in order to assess the composition of the local bacterial community. A research coordinator will also obtain bilateral cultures of each participant's scalp via the RODAC plate method in order to assess the burden of *S. aureus* on the skin. Swab and culture samples will be sent to the lab of [name] at Lurie Children's or to [name] lab at Rush University to be processed via 16s rRNA sequencing and colony count, respectively. Lastly, a board-certified physician will assess the clinical severity of the participant's dry scalp via the 11-point flaking scale. Photographs will be taken as record for both adult and child studies.

Each participant will then fill out a baseline survey including demographics in REDCap.

Participants will be supplied with the scalp treatment and relevant instructions. Participants will be instructed to apply the preparation to their scalp. Adults will apply the scalp treatment on the site of active dry scalp once per day at home at a consistent time, every day for 14 days. Children will apply the hair care regimen at home at a consistent time two to three times a week over a 14-day period. -. Participants will be instructed to discontinue their regular scalp-care therapies. Adult participants will be contacted daily via email or telephone regarding scalp care regimen, usage of treatment, and any adverse events. Child participants will be contacted weekly via email or text regarding scalp care regimen, usage of treatment, and any adverse events. One week from the baseline visit (7 days), the participant will be contacted via phone, text or email to complete surveys regarding treatment experience and to confirm correct usage of treatment. Fourteen days following the baseline visit, adult participants will be seen, where repeat scalp cultures will be obtained via the swab and RODAC methods, and a repeat scalp flaking survey (IGA) (with photographs) will be assessed by a physician. Final experience surveys will be administered via REDCap. Fourteen days following the baseline visit, child participants will attend a secondary visit, where a physician will assess the participants' scalp and re-evaluate the IGA placement.

Study Schema

VISIT 1: (baseline)

- Recruitment and electronic informed consent of participants via REDCap.
- Obtain baseline scalp culture skin swabs from participant for microbiome diversity analysis.
- Obtain baseline scalp cultures from participant via RODAC method to obtain initial bacterial burden level. The RODAC (Replicate Organism Detection and Counting) method is used to measure the number of colony forming units (CFU) per skin surface area. The primary purpose of the RODAC method is to monitor presence and number of microorganisms as determined by the appearance of colonies on the surface of an agar medium.
- Local scalp flaking survey performed to the participant by investigator. Photographs will be taken.
- Administer baseline demographics survey via REDCap.
- Demonstrate/teach patients the treatment regimen. The treatment for adults will be applied daily for 14 days for 5 minutes. The treatment for children will be applied 2 to 3 times a week over the course of 14 days for 5 minutes.
- Instruct adult participants to respond to the daily scalp care emails or phone calls. Instruct child participants to weekly scalp care emails, text messages, or phone calls.- Provide participants with all study materials, including instruction handout.
- Instructions for adults will be given stating: Wash your hands and make sure scalp/hair is dry, and then apply the treatment to your entire scalp. Massage the treatment in, wait around seven minutes, and then rinse it from your scalp. Please be sure to apply the treatment daily. Instructions for children will be given stating: Wash your hands and make sure scalp/hair is dry, and then apply the treatment to your entire scalp. Massage the treatment in, wait approximately five minutes, and then rinse it from your scalp. Please be sure to apply the treatment 2 to 3 times a week.

FOLLOW-UP:

- Study coordinator will contact participant or caregiver via phone or email daily to ensure safety of treatment regimen. [name] will follow-up with patients if adverse events are reported.
- Quality of life and overall safety score surveys will be sent to participants at the 7 day mark.

VISIT 2 at Lurie Children's, Northwestern University, or Medical Dermatology Associates of Chicago: (14 days after baseline)

- Obtain scalp culture skin swabs from patient for microbiome diversity analysis.
- Obtain scalp cultures from patient via RODAC method to obtain final bacterial burden level.

- Local scalp flaking survey performed to patient by investigator. Additional photographs will be taken.
- Ask participants to fill out the follow-up questionnaire via REDCap during the visit on a study iPad.

Events performed outside of patient visits:

-Skin swabs and RODAC plates will be transported from the collection site to the laboratory of [name] or to [name] lab at Rush University. The team will use an insulated carrier to transport the samples directly following each visit.

For visit 1 and 2, the study visit will take place at either Lurie Children's, Northwestern University, Children's Healthcare Associates, or Medical Dermatology Associates of Chicago. A board certified Dermatologist, Allergist, or Physician/pediatrician will conduct a scalp assessment to determine whether the participant is eligible for the study. [name], the PI, will be the primary contact in the event of an adverse event, but will not be involved directly with any items in visit 1, the follow up, or visit 2. A research coordinator will consent the participant, explain the procedures of the study, swab the scalp, and administer the surveys. Either a research coordinator or physician will take pictures of the patient's scalp. The same responsibilities for the physician and research coordinator will take place at visit 2. For the adult follow ups, a research coordinator will either email or call the participant daily (based off their preference) regarding treatment use and adverse effects. Storage will occur at [name] Lab (Lurie Children's) and [name] lab at Rush University, and analysis will be done by [name] lab and [name] lab at Rush University.

Parents will be asked to perform the treatment on children ages 1-11, but children ages 12 years-17 years will be asked to perform the treatment themselves. Parents will complete surveys for all children regardless of age.

6. DATA COLLECTION AND REPORTING:

At baseline, culture swabs will be obtained from all patients' scalp via both the swab and RODAC method. Patients will fill out an intake survey including demographics via REDCap. The physician will complete a scalp flaking survey to evaluate initial disease severity.

At the 7-day mark, adult patients will be emailed or texted surveys to ensure the treatment regimen and daily instructions are being completed correctly as well as to assess the safety and efficacy of the treatment. At the 7-day mark, child patients will be emailed or texted surveys to ensure the treatment regimen and weekly instructions are being completed correctly as well as to assess the safety and

efficacy of the treatment. All questions will be answered and noted on a secure Northwestern server.

At the 14-day follow-up visit, cultures will again be obtained from the patients' scalp via the swab and RODAC methods. The investigator will complete the scalp flaking survey to evaluate endpoint disease severity. Patients will then fill out a follow-up questionnaire via REDCap.

At the 14-day follow-up visit for child participants, the investigator will complete the scalp flaking survey to evaluate endpoint disease severity. Patients will then fill out a follow-up questionnaire via REDCap.

Participants will only be identified via their coded numeric subject ID. The document linking the code to the participant will be stored on a secure Northwestern server and all study team members will have access to the server.

Informed consent and all surveys will be programmed into REDCap NUBIC by a member of the study team. All other data will be stored in an electronic database and stored on a secure Northwestern server. Only those outlined in the IRB will have access to the information.

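### The plan places the flaking score and photographs after scalp swabs and contact plates; score and photograph first, and settle whether children are sampled at day 14

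*Combined protocol and SAP*

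**What the plan says.** The baseline procedures in Section 5 (Study Procedures) begin with the coordinator's sampling: "A research coordinator will obtain bilateral culture swabs of the scalp", and then "A research coordinator will also obtain bilateral cultures of each participant's scalp via the RODAC plate method". After a sentence on sending samples to the laboratories comes the score: "Lastly, a board-certified physician will assess the clinical severity of the participant's dry scalp via the 11-point flaking scale". Photographs follow: "Photographs will be taken as record for both adult and child studies".

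The Study Schema repeats this order. At Visit 1, after the swab and RODAC items, it lists "Local scalp flaking survey performed to the participant by investigator. Photographs will be taken". At Visit 2, again after swabs and RODAC, it lists "Local scalp flaking survey performed to patient by investigator. Additional photographs will be taken".

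For day 14, Section 5 separates the age groups. The adult sentence describes a visit "where repeat scalp cultures will be obtained via the swab and RODAC methods, and a repeat scalp flaking survey (IGA", with photographs. The child sentence says "child participants will attend a secondary visit, where a physician will assess the participants' scalp and re-evaluate the IGA placement" and mentions no sampling.

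The flaking score carries the efficacy claim: it is the measure in the first goal (Section 2), Hypothesis 1a (Section 3) and Section 8. Section 6.1 names other scales, but also lists a scaling component and before/after photographs under efficacy.

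**The concern.** Swabbing and pressing agar plates onto a flaking scalp could remove, loosen or redistribute scale, and visible scale is what the physician then rates. This is an inference from the procedure; the documents do not discuss it. They also do not separate sampled from scored areas, set an interval between sampling and scoring, or define the site of the local flaking survey.

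The study has one arm and no randomisation (Section 2), so the only efficacy contrast is each participant's change from baseline to day 14. No control group shares the disturbance. Photographs taken after sampling could not serve as an undisturbed record against which to check the score. The stake is greatest if one visit is sampled and the other is not.

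**Working it through.** **Step 1: order of steps, place by place.**

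| Place | Order given | Photographs |
|---|---|---|
| Section 5, baseline text | swabs, RODAC, *lastly* the score, then survey | after the score |
| Schema, Visit 1 | swabs, RODAC, score, survey | with the score |
| Schema, Visit 2 | swabs, RODAC, score, questionnaire | with the score |
| Section 5, adult day 14 | cultures, score | with the score |
| Section 6, baseline | swabs and RODAC, intake survey, score | not mentioned |
| Section 6, day 14 (general) | cultures, score, questionnaire | not mentioned |
| Section 5, staff roles | physician's eligibility assessment, then coordinator's consent and swabs | after the swabs; coordinator or physician |

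No place puts the recorded flaking score or the photographs before sampling. The physician's assessment in the staff-roles text is for eligibility and is not described as the recorded score. The word *lastly* in Section 5 is the firmest evidence, because the schema items are not numbered.

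**Step 2: sampling of children.** Section 6 has all patients swabbed and plated at baseline. At day 14 the child sentence in Section 5 and the child paragraph in Section 6 describe scoring without sampling. The Visit 2 list, and the general day-14 paragraph in Section 6, have sampling with no age limit. These cannot all be followed.

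**Step 3: how a sampling effect would enter the change.** Let the true scores be S0 and S14 and the true fall D = S0 − S14. Let e0 and e14 be the amounts by which sampling lowers the recorded score at each visit (negative if it raises it). Then

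observed fall = (S0 − e0) − (S14 − e14) = D − (e0 − e14).

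- Both visits sampled first: the error is e0 − e14. A constant effect cancels, except where scores are already near zero. If sampling differs between visits, the difference becomes noise.
- Only baseline sampled first: e14 = 0, so the error is the whole of e0.

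**Step 4: illustration.** The documents give no figure to reproduce for this effect. *Assumptions, not from the documents:* sampling changes the score by a fraction f, so e = f × S; the true fall is D = 1 point; baseline B is 3 or 5. The formulas become

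- both visits sampled: (1 − f) × D
- baseline only: D − f × B

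| f | Both sampled | Baseline only, B = 3 | Baseline only, B = 5 |
|---|---|---|---|
| −10% (score raised) | 1.10 | 1.30 | 1.50 |
| 0 | 1.00 | 1.00 | 1.00 |
| 5% | 0.95 | 0.85 | 0.75 |
| 10% | 0.90 | 0.70 | 0.50 |
| 20% | 0.80 | 0.40 | 0.00 |

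Example: with f = 10% and B = 5, baseline is recorded as 0.9 × 5 = 4.5 and day 14 as 4, so the observed fall is 0.5.

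The one-point fall echoes the difference named in Section 10.1, but that section refers to a 5-point scale and the flaking scale has 11 points. It serves here only as a unit for the illustration.

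**The case against.** The strongest reply is that these lists are inventories and not timed sequences. In Section 5, *lastly* follows a sentence on laboratory processing, which cannot happen before the score, so that paragraph is not strictly chronological. Section 6 puts the intake survey before the score, whereas Section 5 and the Visit 1 list put it after. A reader might infer that Section 6 confirms the full sequence of swab, plate, score and photograph; it does not, since it mentions no photographs and differs on the survey. This part of the reply stands in so far as the order is less firm than a numbered schedule would make it. It does not remove the point: every list that includes both puts sampling before the score, and none says otherwise.

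The second reply is that the mechanism is assumed. Swab technique, sampled area and scored region are not given, so an 11-point rating may not move at all. This stands. A reader might infer a known loss of a particular number of points, or a bias known to run against the product. The documents support neither: scale that is moved or loosened need not lower the rating.

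The third reply is that adults are handled alike at both visits. This stands for the mean change, apart from the limited shrinkage and noise shown above.

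Finally, a reader might infer that children are definitely unsampled at day 14. The Visit 2 list and the general day-14 paragraph of Section 6 do not support that. It is an unresolved conflict.

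**Conclusion.** The point holds as an inexpensive improvement to visit order, together with a conflict over children that needs settling. As written, the efficacy score and photographs come after a procedure that could disturb what they record. The size and direction are unknown, and zero is possible.

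For adults the consequence is small, provided sampling is done alike at both visits: under a proportional loss of 5% to 20%, a one-point fall would read as 0.95 to 0.80. For children the consequence depends on which text is followed. If they are sampled at both visits, the adult reasoning applies. If they are sampled only at baseline, any effect enters the change in full; for the same assumed losses the reading is 0.85 to 0.40 at a baseline of 3, and 0.75 to 0 at a baseline of 5. If sampling raised the score, improvement would be overstated instead. These figures rest on assumed values of f and B and are not estimates for this trial.

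**What to change.** 1. In Section 5 (baseline and day-14 text) and in the Visit 1 and Visit 2 lists, state one order for both visits and all ages, after consent: physician's flaking score, photographs, swabs, RODAC plates. Ask for minimal or gloved handling of the scalp before sampling.
2. Record the baseline score only after consent. Simply reusing the eligibility assessment could place outcome collection before consent: Section 5 has patients invited after a regular appointment, the Visit 1 list puts consent first, and Section 13.2 requires it before study entry.
3. Reconcile the child day-14 text in Sections 5 and 6 with the Visit 2 list and the general day-14 paragraph of Section 6, so that it is clear whether children are sampled at day 14.

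The cost is low: no added procedure, visit or participants. There are two small downsides. The physician must be available before sampling, and the scalp is handled slightly before the microbiome samples. The second is acceptable because the microbiome aim is exploratory (Sections 2 and 6.1), whereas the score carries the efficacy claim.
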